18. APPENDIX 1: GUIDANCE ON STUDY CONDUCT DURING THE COVID-19 PANDEMIC

It is recognized that the Coronavirus Disease 2019 (COVID-19) pandemic may have an impact on the conduct of this clinical study due to, for example, self-isolation/quarantine by participants and study-site personnel; travel restrictions/limited access to public places, including hospitals; study site personnel being reassigned to critical tasks.

In alignment with recent health authority guidance, the sponsor is providing options for study related participant management in the event of disruption to the conduct of the study. This guidance does not supersede any local or government requirements or the clinical judgement of the investigator to protect the health and well-being of participants and site staff. If, at any time, a participant's safety is considered to be at risk, study intervention will be discontinued, and study follow-up will be conducted.

Scheduled visits that cannot be conducted in person at the study site will be performed to the extent possible remotely/virtually or delayed until such time that on-site visits can be resumed. At each contact, participants will be interviewed to collect safety data. Key efficacy endpoint assessments should be performed if required and as feasible. Participants will also be questioned regarding general health status to fulfill any physical examination requirement.

Every effort should be made to adhere to protocol-specified assessments for participants on study intervention, including follow up. Modifications to protocol-required assessments may be permitted via COVID-19 Appendix after consultation with the participant, investigator, and the sponsor. Missed assessments/visits will be captured in the clinical trial management system for protocol deviations. Discontinuations of study interventions and withdrawal from the study should be documented with the prefix "COVID-19-related" in the case report form (CRF).

The sponsor will continue to monitor the conduct and progress of the clinical study, and any changes will be communicated to the sites and to the health authorities according to local guidance. If a participant has tested positive for COVID 19, the investigator should contact the sponsor's responsible medical officer to discuss plans for study intervention and follow-up. Modifications made to the study conduct as a result of the COVID-19 pandemic should be summarized in the clinical study report.

GUIDANCE SPECIFIC TO THIS PROTOCOL:

- When site visits are not possible due to local/national guidelines, sites should collect the assessments via telephone visits or home-based visits, if the participant allows. The actual visit date and the type of visit (ie, telephone or home-based visit) should be captured in the eCRF. Procedures that cannot be performed during a home-based visit (eg, clinical assessments, blood samples, nasal samples and physical examination), should be excluded. The missed procedures should be recorded as "missed due to COVID-19".
- When planning for vaccination visits, local/national or institutional guidelines will be followed. The study vaccine should be administered by an (unblinded) pharmacist or other

qualified individual at the study site. If this is not possible, a solution may be considered in consultation with the sponsor and taking into consideration participant safety. Of note, if a scheduled study vaccination is not possible at the scheduled visit time, the vaccination should occur within 3 weeks after the scheduled visit.

- A revised ICF arising from this amendment needs to be signed by the participants during a site visit or home-based visit, if the participant allows. When a site or home-based visit is not possible due to local/national guidelines, the participant can sign the paper ICF and mail the signed document to the site.

REFERENCES

Attachment 1: Toxicity Tables

Adapted from the FDA Guidance document “Toxicity Grading Scale for Healthy Adult and Adolescent Volunteers Enrolled in Preventive Vaccine Clinical Trials” (September 2007).

A: Tables for Clinical Abnormalities

Local Reaction to Injectable Product	Mild (Grade 1)	Moderate (Grade 2)	Severe (Grade 3)	Potentially Life-threatening (Grade 4)
Pain	Does not interfere with activity	Repeated use of non-narcotic pain reliever > 24 hours or interferes with activity	Any use of narcotic pain reliever or prevents daily activity	Emergency room (ER) visit or hospitalization
Tenderness	Mild discomfort to Touch	Discomfort with Movement	Significant discomfort at rest	ER visit or Hospitalization
Erythema/redness*	2.5 – 5 cm	5.1 – 10 cm	> 10 cm	Necrosis or exfoliative dermatitis
Induration/swelling**	2.5 – 5 cm and does not interfere with activity	5.1 – 10 cm or interferes with activity	> 10 cm or prevents daily activity	Necrosis

* In addition to grading the measured local reaction at the greatest single diameter, the measurement should be recorded as a continuous variable.

** Induration/Swelling should be evaluated and graded using the functional scale as well as the actual measurement.

Vital Signs *	Mild (Grade 1)	Moderate (Grade 2)	Severe (Grade 3)	Potentially Life-threatening (Grade 4)
Fever** (°C)	38.0 – 38.4	38.5 – 38.9	39.0 – 40	> 40
Fever** (°F)	100.4 – 101.1	101.2 – 102.0	102.1 – 104	> 104
Tachycardia - beats per minute	101 – 115	116 – 130	> 130	ER visit or hospitalization for arrhythmia
Bradycardia - beats per minute***	50 – 54	45 – 49	< 45	ER visit or hospitalization for arrhythmia
Hypertension (systolic) - mm Hg****	141 – 150	151 – 160	> 160	ER visit or hospitalization for malignant hypertension
Hypertension (diastolic) - mm Hg	91 – 95	96 – 100	> 100	ER visit or hospitalization for malignant hypertension
Hypotension (systolic) - mm Hg	85 – 89	80 – 84	< 80	ER visit or hospitalization for hypotensive shock
Respiratory rate - breaths per minute	17 – 20	21 – 25	> 25	Intubation

* Participant should be at rest for all vital sign measurements.

** Oral body temperature; no recent hot or cold beverages or smoking.

*** When resting heart rate is between 60 and 100 beats per minute. Use clinical judgment when characterizing bradycardia among some healthy participant populations, for example, conditioned athletes.

**** Revised by the sponsor.

Systemic (General)	Mild (Grade 1)	Moderate (Grade 2)	Severe (Grade 3)	Potentially Life-threatening (Grade 4)
Nausea/vomiting	No interference with activity or 1 - 2 episodes/24 hours	Some interference with activity or > 2 episodes/24 hours	Prevents daily activity, requires outpatient IV hydration	ER visit or hospitalization for hypotensive shock
Diarrhea	2 - 3 loose stools or < 400 gms/24 hours	4 - 5 stools or 400 - 800 gms/24 hours	6 or more watery stools or > 800 gms/24 hours or requires outpatient IV hydration	ER visit or hospitalization
Headache	No interference with activity	Repeated use of non-narcotic pain reliever > 24 hours or some interference with activity	Significant; any use of narcotic pain reliever or prevents daily activity	ER visit or hospitalization
Fatigue	No interference with activity	Some interference with activity	Significant; prevents daily activity	ER visit or hospitalization
Myalgia	No interference with activity	Some interference with activity	Significant; prevents daily activity	ER visit or hospitalization
Systemic Illness	Mild (Grade 1)	Moderate (Grade 2)	Severe (Grade 3)	Potentially Life-threatening (Grade 4)
Illness or clinical adverse event (as defined according to applicable regulations)	Awareness of symptoms that are easily tolerated, causing minimal discomfort and not interfering with everyday activities	Sufficient discomfort is present to cause interference with normal activity	Extreme distress, causing significant impairment of functioning or incapacitation. Prevents normal everyday activities	Symptoms causing inability to perform basic self-care functions OR medical or operative intervention indicated to prevent permanent impairment, persistent disability

B: Tables for Laboratory Abnormalities

The grading scale used for laboratory assessments is based on the FDA Guidance document “Toxicity Grading Scale from Healthy Adult and Adolescent Volunteers Enrolled in Preventive Vaccine Clinical Trials”. Any laboratory value shown as a “graded” value in the table that is within the central laboratory normal ranges will not be graded for severity or recorded as an AE. For hemoglobin, both the actual value and the change from reference will be graded. For the change from reference, the corresponding actual value should also be at least Grade 1.

Serum *	Mild (Grade 1)	Moderate (Grade 2)	Severe (Grade 3)	Potentially Life- threatening (Grade 4) **
Sodium - hyponatremia - mEq/L	132 – 134	130 – 131	125 – 129	< 125
Sodium - hypernatremia - mEq/L	144 – 145	146 – 147	148 – 150	> 150
Potassium - hyperkalemia - mEq/L	5.1 – 5.2	5.3 – 5.4	5.5 – 5.6	> 5.6
Potassium - hypokalemia - mEq/L	3.5 – 3.6	3.3 – 3.4	3.1 – 3.2	< 3.1
Glucose - hypoglycemia - mg/dL	65 – 69	55 – 64	45 – 54	< 45
Glucose - hyperglycemia fasting - mg/dL	100 – 110	111 – 125	> 125	Insulin requirements or hyperosmolar coma
Random glucose - mg/dL	110 – 125	126 – 200	> 200	
Blood urea nitrogen BUN - mg/dL	23 – 26	27 – 31	> 31	Requires dialysis
Creatinine - mg/dL	1.5 – 1.7	1.8 – 2.0	2.1 – 2.5	> 2.5 or requires dialysis
Calcium - hypocalcemia - mg/dL	8.0 – 8.4	7.5 – 7.9	7.0 – 7.4	< 7.0
Calcium - hypercalcemia - mg/dL	10.5 – 11.0	11.1 – 11.5	11.6 – 12.0	> 12.0
Magnesium - hypomagnesemia - mg/dL	1.3 – 1.5	1.1 – 1.2	0.9 – 1.0	< 0.9
Phosphorous - hypophosphatemia - mg/dL	2.3 – 2.5	2.0 – 2.2	1.6 – 1.9	< 1.6
CPK - mg/dL	1.25 – 1.5 x ULN***	1.6 – 3.0 x ULN	3.1 – 10 x ULN	> 10 x ULN
Albumin - Hypoalbuminemia - g/dL	2.8 – 3.1	2.5 – 2.7	< 2.5	--

Serum *	Mild (Grade 1)	Moderate (Grade 2)	Severe (Grade 3)	Potentially Life- threatening (Grade 4) **
Total protein - hypoproteinemia - g/dL	5.5 – 6.0	5.0 – 5.4	< 5.0	--
Alkaline phosphate - increase by factor	1.1 – 2.0 x ULN	2.1 – 3.0 x ULN	3.1 – 10 x ULN	> 10 x ULN
Liver function tests - ALT, AST increase by factor	1.1 – 2.5 x ULN	2.6 – 5.0 x ULN	5.1 – 10 x ULN	> 10 x ULN
Bilirubin - when accompanied by any increase in liver function test increase by factor	1.1 – 1.25 x ULN	1.26 – 1.5 x ULN	1.51 – 1.75 x ULN	> 1.75 x ULN
Bilirubin – when liver function test is normal; increase by factor	1.1 – 1.5 x ULN	1.6 – 2.0 x ULN	2.0 – 3.0 x ULN	> 3.0 x ULN
Cholesterol	201 – 210	211 – 225	> 226	--
Pancreatic enzymes - amylase, lipase	1.1 – 1.5 x ULN	1.6 – 2.0 x ULN	2.1 – 5.0 x ULN	> 5.0 x ULN

* The laboratory values provided in the tables serve as guidelines and are dependent upon central laboratory normal parameters. Central laboratory normal reference ranges should be provided to demonstrate that they are appropriate.

** The clinical signs or symptoms associated with laboratory abnormalities might result in characterization of the laboratory abnormalities as potentially life-threatening (Grade 4). For example, a low sodium value that falls within a Grade 3 parameter (125-129 mE/L) should be recorded as a Grade 4 hyponatremia event if the participant had a new seizure associated with the low sodium value.

*** ULN is the upper limit of the normal range.

The overall reason for the amendment: The SAP was amended to add clarifications on the ‘Transforming the on-site assessments and diaries of solicited AEs into analysis format’ text and to further clarify which visits will be used to create the summary table of the reported temperatures.

Other minor corrections in punctuation were made throughout the document.

Find below the sections that are affected:

5.3 Vital Signs and Physical Examination Findings

ATTACHMENT 2: Transforming the on-site assessments and diaries of solicited AEs into analysis format

Amendment 2(Creation date: 16/03/2021)

The overall reason for the amendment: To include the protocol-defined visit windows for the per-protocol immunogenicity analysis. Records outside the protocol-defined visit windows will not be included in the per-protocol immunogenicity analysis. The definition of the per-protocol immunogenicity set was also amended: instead of excluding the whole participant from the analysis for participants experiencing a major protocol deviation (MPD) expected to impact immunogenicity outcomes, only samples occurring after the MPD will be excluded.

Find below the sections that are affected:

2.1.2 Visit Windows

2.3 Analysis Sets

Amendment 3(Creation date: 09/02/2022)

The overall reason for the amendment: To align with the clinical trial protocol amendment 6. The concomitant medication section was also updated to align with other RSV vaccine (VAC18193) SAPs. The solicited adverse event SDTM datasets (FA/SR) were remapped to a new structure/model (FA/CE). Therefore, the adverse events section (and attachment 2) of the current SAP was updated to align with the remapping. Analysis of potential adverse events of special interest (AESI) and subgroup analysis were added to the safety analysis. There were minor updates in Section 6.1 to clarify the intracellular cytokine staining (ICS) analysis. The imputation rule of immunogenicity values above the upper limit of quantification (ULOQ) was updated to align with other RSV vaccine (VAC18193) SAPs.

Definition of time intervals for AESIs was added.

Find below the sections that are affected:

1.2 Trial Design

2.1.1 Phase definitions

2.4 Definition of Subgroups

4.4 Concomitant medications**5.1.1 Definitions****5.1.2 Analysis of Adverse Events****5.1.3 Phase allocation of adverse events****6.1 Secondary and Exploratory Endpoints****6.1.2 Handling of Missing and/or Unquantifiable Immune Response Data****ATTACHMENT 2: Transforming Solicited AE data into Analysis Format**

Amendment 4 (Creation date: 28/03/2022)

The overall reason for the amendment: to clarify the protocol-defined visit windows for the per-protocol immunogenicity analysis in case of missing vaccination. Records outside the protocol-defined visit windows will not be included in the per-protocol immunogenicity analysis. In case of missing vaccination, the windows should be based on the day of this missing vaccination. The windows were also updated to align with study protocol.

Methods to define potential AESIs were updated.

Find below the sections that are affected:

2.1.2 Visit Windows**5.1.2 Analysis of Adverse Events**

1. INTRODUCTION

This is the Statistical Analysis Plan (SAP) applicable for the VAC18193RSV1004 trial, for all analyses of the initial safety, the regimen selection and the expanded safety cohorts mentioned in Section 11.6.1, 11.6.2 and 11.6.3 of the clinical trial protocol (CTP). This SAP will also be used as a guideline for any ad-hoc analyses of these cohorts too.

1.1. Trial Objectives

Please refer to Section 2.1 in the CTP.

1.2. Trial Design

Refer to Section 3.1.1 of the CTP.

1.3. Statistical Hypotheses for Trial Objectives

No formal statistical testing is planned in the initial safety cohort (Cohort 1), in the regimen selection cohort (Cohort 2) and in the expanded safety cohort (cohort 3).

1.4. Sample Size Justification

Please refer to Section 11.2 from the CTP.

1.5. Randomization and Blinding

Please refer to Section 5 from the CTP.

1.6. Changes to Planned Analysis

The Per-protocol Immunogenicity Analysis

Instead of excluding the whole participant data from the per-protocol analysis, the following will be done:

If a participant's immunogenicity sample is collected out of the protocol-defined visit window, the sample will be excluded from the per-protocol analysis. All the other samples (from the same participant) that are not impacted will be included in the per-protocol analysis (Section 2.1.2).

Samples taken after a participant experienced a major protocol deviation expected to impact the immunogenicity outcomes will be excluded from the per-protocol analysis (Section 2.3). All other samples (from the same participant) collected before the deviation (that are not impacted) will be included in the per-protocol analysis.

Imputation Rule for Immunogenicity values above the upper limit of quantification (ULOQ)

The imputation rule for immunogenicity values above the ULOQ was updated to align with other RSV vaccine (VAC18193) SAPs. Values above the ULOQ will be imputed with the ULOQ values instead of 2xULOQ.

2. GENERAL ANALYSIS DEFINITIONS

2.1. Study phases

A baseline (or reference) value will be defined as the value of the last available assessment prior to the first vaccination on Day 1.

The safety analysis will present all results by period, except the serious adverse events (SAE) that will be presented by phase and period (See Section 0). Immunogenicity results will be presented per scheduled time point as appropriate. Listings will be shown per phase and time point.

Study day or relative day is defined as follows:

Study Day = visit date - date of Day 1 + 1; if visit date \geq date of Day 1 (date of first vaccination).

Study Day = visit date - date of Day 1; if visit date $<$ date of Day 1 (date of first vaccination).

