9.1.5. Vaccination

On each vaccination day according to the schedules presented in Table 8, Table 9, Table 10 and Table 11, the following procedures will apply pre- and post-vaccination:

- Pre-vaccination, verification of selected inclusion/exclusion criteria,^a physical examination,^b and measurement of vital signs will be performed for all participants.
- Pre-vaccination, blood and nasal samples will be collected for immunogenicity assessments. In Cohorts 1 and 2, pre-dose blood samples will be taken on Day 1 for transcriptome analysis and safety laboratory tests (hematology and biochemistry).
- Pre-vaccination, the investigator must check for any symptoms of acute illness or fever (body temperature ≥ 38.0 °C). In such a situation, the participant may be vaccinated up to, and no later than 10 days after the scheduled vaccination, or withdrawn from further vaccination at the discretion of the investigator.
- Post-vaccination, participants will be closely observed for at least 30 minutes to monitor for development of any acute reactions, or longer if deemed necessary by the investigator. Vital signs measurement will be performed. Any unsolicited or solicited AEs and vital signs will be documented in the eCRF by study-site personnel following this observation period.
- All participants will be provided with a participant diary, thermometer, and ruler to measure and record body temperature, and solicited local and solicited systemic AEs for 7 days post-vaccination.
- Nasal swab kits and RTI Symptoms Forms will be distributed to all participants before the start of the first 2 RSV seasons of the study (relative to the enrollment date of the first participant in Cohort 1); during these RSV seasons, participants should record signs and symptoms of RTI using the RTI Symptoms Form.

^a To include receipt of any routine immunizations.

^b A full physical examination, including height and body weight, will be carried out at screening, and before final vaccination. At other vaccination visits, an abbreviated, symptom-directed examination will be performed if determined necessary by the investigator.

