Regimen	2	Post-Boost (Month 24)	4	Date and time of Month 24 Boost	Minimum of: a) 23:59 at the date of database cut-off b) Maximum (28 days after the Month 24 boost vaccination at 23.59, scheduled visit 4 weeks after the Month 24 boost vaccination at 23:59) c) 23:59 at the date of last contact (for completed and early discontinuation of the study)

Table 1: Phase Definitions of Cohort 1, 2 and 3

Phase	Phase number	Period	Period number	Interval	
				From	To
Follow-Up Boost (Month 24)	6			1 minute after end of Post-Boost (Month 24) period	Minimum of: a) 23:59 at the date of database cut-off b) 23:59 at the date of last contact (for completed and early discontinuation of the study)

^a in case an earlier date is available (eg. for lab or vital signs), then use the very first date to include all data

In case the one-dose regimen is selected (Groups 11 through 16 from Cohort 2) after the evaluation of Cohort 2, then the post dose 2 and follow up 2 will not be applicable.

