5. SAFETY

Safety analyses will be performed on the FA set. Continuous variables will be summarized using the following statistics, as appropriate: number of observations, median, quartiles (Q1 and Q3), minimum and maximum. Frequencies and percentages (one decimal place) will be generated for categorical variables. No formal comparisons between groups will be provided.

One type of safety tables will be shown. The by regimen layout, safety data will be analysed by vaccine regimens as designed per protocol and data will be presented by period. Denominator for the percentages is the number of subjects with considered data in the considered population and period for a certain regimen (incidence per 100 subjects/period).

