5.2. Clinical Laboratory Tests

For laboratory safety parameters, only abnormalities emerging will be tabulated by worst abnormality grade using the modified FDA table in [ATTACHMENT 1](#).

An abnormality (toxicity grade or abnormality based on normal ranges) will be considered as emerging in a particular period if it is worse than the baseline value. If the baseline is missing, the abnormality is always considered emerging. A shift from ‘abnormally low’ at baseline to ‘abnormally high’ post baseline (or vice versa) is also emerging. In case a laboratory test result is censored (no numeric value is available, but only a verbatim term) then a numeric value will be imputed by a value exceeding the cut-off value with one unit. ($<x$: subtract 1 unit from x , $>x$: add 1 unit to x ; <3.45 is imputed with 3.44).

In case no toxicity grades are defined for a test, the abnormalities (above/below normal range) will be used. In determining toxicity grades, the following rules are applied:

- worst grades/abnormalities are determined over the whole observational period for each trial period separately, including all post-baseline measurements of that period.
- The abnormalities ‘abnormally low’ and ‘abnormally high’ are considered equally important, i.e. if a subject has as well an abnormally low as an abnormally high value post-baseline, both abnormalities are shown in the tables. (This means that the sum of the percentages can be more than 100%)
- Note: as the grading scale for some parameters in the grading table has some gaps (zones where no toxicity grade definition exists), laboratory results falling in these zones will be allocated to the adjacent worst-case grade.
- If a laboratory value falls within the grading as specified in the grading table but also within the local lab normal limits, the value is considered as normal.
- HGB: for hemoglobin grades are based on both actual values and changes. Those grading will be listed separately. In addition, for the grading on the changes of HGB, the corresponding actual value should be at least grade 1.
- Only the lab values are used in determining the toxicity grades. For some lab parameters, extra clinical assessments are available to attribute grade 4 toxicity (eg. requiring hospitalization or dialysis), but these are not taken into account in the lab analysis

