5.3. Vital Signs, Physical Examination Findings and Electrocardiogram (ECG)

Similar to laboratory tests, only vital signs abnormalities emerging after vaccination will be tabulated by worst abnormality grade. a

Heart rate (beats per minutes, bpm), respiratory rate (breaths per minute), systolic blood pressure (mmHg) and diastolic blood pressure (mmHg) will be collected. The respective vital signs abnormalities are defined in Table 5. Moreover, only the vital signs values will be used, no clinical interpretations, therefore, grade 3 and 4 is shown combined as grade 4 always requires clinical interpretation.

Table 5: Vital Signs Toxicity

Vital Signs	Grade 1	Grade 2	Grade 3 /4
Tachycardia – beats (HR) per minute	101 – 115	116 – 130	>130
Bradycardia – beats (HR) per minute	50 – 54	45 – 49	< 45
Hypertension (systolic) - mm Hg	141 – 150	151 – 160	>160
Hypertension (diastolic) - mm Hg	91 – 95	96 – 100	>100
Hypotension (systolic) - mm Hg	85 – 89	80 – 84	< 80
Respiratory Rate - breaths per minute	17-20	21-25	>25

Temperature from diary, on-site assessments from day of vaccination and any on-site assessment performed between the vaccination visit and the visit 7 days post-vaccination (from 37.5° C until 40°C, in steps of half degree increments, e.g., <37.5, 37.5-<38, 38-<38.5, ... >40). A table will be created, showing the maximum temperature for both diary and onsite assessments combined.

Any abnormal physical examination result will be documented as AEs, by the investigator. For Cohorts 1 and 2, any abnormalities in ECG parameter (at screening) will be listed.

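### SAP 5.3 judges vital signs after the Month 12 and Month 24 boosters against a pre-first-dose value one or two years old, which misclassifies individuals both ways

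*SAP*

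**What the plan says.** Four parts of the SAP have to be read together.

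- **Reference value (SAP 2.1):** "A baseline (or reference) value will be defined as the value of the last available assessment prior to the first vaccination on Day 1". There is one definition, with no variant by dose or period.
- **Meaning of emerging (SAP 5.2):** an abnormality "will be considered as emerging in a particular period if it is worse than the baseline value", and "worst grades/abnormalities are determined over the whole observational period for each trial period separately".
- **Vital signs (SAP 5.3):** "Similar to laboratory tests, only vital signs abnormalities emerging after vaccination will be tabulated by worst abnormality grade". Section 5.3 gives no definition of its own, so it takes the rule from 5.2.
- **Layout (SAP 5 and Table 1 in 2.1.1):** "safety data will be analysed by vaccine regimens as designed per protocol and data will be presented by period". The last boost period starts at "Date and time of Month 24 Boost", and the preceding follow-up phase ends one minute earlier.

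On data collection, Protocol 9.1.5 covers each vaccination day. Before the injection, eligibility checks, physical examination "and measurement of vital signs will be performed for all participants"; vital signs are measured again afterwards. Protocol 11.5 plans only the percentage of participants beyond clinically relevant limits and makes no baseline comparison.

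**The concern.** A table of abnormalities emerging after a booster should show what changed around that booster. Under these rules it shows what changed since before the first dose. The pre-dose reading at the booster visit falls in the preceding follow-up phase and is never used as a reference.

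Two errors follow. An abnormality that developed in the intervening one or two years and was already present before the booster counts as emerging after it. A new abnormality after the booster that is no worse than the Day 1 value is not counted.

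Both are realistic in this population. Participants are 60 or older, controlled hypertension is allowed, and Protocol 4.1 lets people enrol with Grade 1 or Grade 2 vital signs. Only someone abnormal on Day 1 can be missed in the second way, so that allowance matters.

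The tables also become hard to read across periods, because the Post-Dose 1 reference is normally a same-day value and the booster references are not. The adverse event method differs too: SAP 5.1.3 assigns an unsolicited event to a period by its start date, so a condition that began during follow-up is not a post-booster event there.

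**Working it through.** The documents give no figure for this point, so there is none to reproduce.

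**1. Age of the reference.** Age = day of vaccination − 1, from the visit windows in Protocol 9.1.2. For Cohort 1, two months is taken as 60 days, as in SAP Table 2; the same length is used for Cohort 3.

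| Vaccination | Nominal | Range over the window |
|---|---|---|
| Day 57 (±3 days) | 57 − 1 = 56 days | 53 to 59 |
| Month 12, Cohort 1 (±2 months) | 365 − 1 = 364 days | 304 to 424 |
| Month 12, Cohort 3 (−2 months) | 365 − 1 = 364 days | 304 to 364 |
| Month 24, Cohort 3 one-dose (±30 days) | 730 − 1 = 729 days | 699 to 759 |

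At the visit 28 days after the Month 24 dose the reference is nominally 729 + 28 = 757 days old, and at most 759 + 31 = 790 days.

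**2. The rule applied to two participants** (systolic pressure, grades from SAP Table 5):

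| | Day 1 | Before booster | Worst after booster | Emerging vs Day 1 | Emerging vs pre-dose |
|---|---|---|---|---|---|
| A | Grade 0 | Grade 2 | Grade 2 | yes | no |
| B | Grade 2 | Grade 0 | Grade 2 | no | yes |

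**3. How often this could happen.** Let D be the Day 1 grade, P the grade before the booster and W the worst grade in the period. At Month 24 the period holds four scheduled readings: after the dose and at the 7-, 14- and 28-day visits (Protocol 9.1.6). Month 12 has three, without the 14-day visit. The SAP counts W > D; the alternative counts W > P.

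Assumed inputs, none from the documents:
- systolic mean 130-135 mmHg and SD 14-15;
- correlation with Day 1 of 0.5-0.65;
- correlation of pre-dose with same-day post-dose of 0.8-0.9;
- later visits correlated with the other booster-month readings at between the Day 1 value and the midpoint of those two;
- no vaccine effect and no mean drift.

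The simulation used 400,000 participants per scenario, Table 5 cut-offs and the worst of four readings:

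- P(W > D) − P(W > P): about 0 to 3 percentage points. Each rate lies roughly between a quarter and a half.
- P(W ≤ P given W > D), counted but no worse than pre-dose: about 22-32%.
- P(W ≤ D given W > P), worse than pre-dose but missed: about 20-29%.

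**4. A second model, to test drift.** Assumed: mean 130 or 135, between-person SD 14, visit-to-visit SD 6-12, worst of four readings.

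- No change over two years: the two overall rates agree, and 6.5-10.9% of all participants are misclassified in each direction. With mean 130 and visit-to-visit SD 8, 30.6% emerge against Day 1 and 7.2% are counted only against Day 1, so 7.2 / 30.6 = 24%, in line with step 3.
- Individual change with mean 0-5 mmHg and SD 8-10: the Day 1 rate exceeds the pre-dose rate by about 2 to 16 points (lowest 47.1 − 44.9 = 2.2; highest 48.7 − 33.0 = 15.7).

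**The case against.** The best defence is that a single pre-first-dose baseline is a recognised convention for change over a whole study, and that it shows persistence: an abnormality that arises after one dose and lasts until the next stays visible. This stands. It is a reason to keep the Day 1 tabulation, but not to make it the only one in a table laid out by dose.

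Second, every arm shares the reference, so common drift appears under placebo. This partly stands. In Cohort 3, Groups 20 and 21 (135 + 45 = 180) receive placebo at Month 12, but at Month 24 only Group 21 (45) does, against 270 on active vaccine. A placebo column can show average drift; it cannot correct individual classifications, and SAP 5 plans no formal group comparison.

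Third, Protocol 9.2.3.4 has clinically significant vital-sign changes reported as adverse events, which need no Day 1 comparison. This stands and limits what could be lost.

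A reader might infer that the booster tables will report far too many events. A calculation with one same-day reading after the booster encourages this: on the same assumptions, 43-63% of those counted would be no worse than pre-dose, and 27-36% of those worse would be missed. But SAP 5.2 takes the worst grade over all readings in the period, which brings the overall rates close together. A large excess needs a two-year rise in blood pressure, for which the documents give no figure.

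**Conclusion.** The point holds as a weakness of the by-period vital-sign tables. No passage supplies a booster-specific reference, and the better one is already collected. It bears on Month 12 in Cohorts 1 and 3, Month 24 in the Cohort 3 one-dose regimen and, less so, the Day 57 dose. That sections 2.1, 5.2 and 5.3 combine in this way is a matter of text; the 22-32% and 20-29% shares are illustrations that rest on assumed inputs.

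Two wider conclusions might be drawn, and the documents do not support them. One is that the Cohort 3 primary safety endpoints are compromised: those listed are serious, solicited and unsolicited adverse events, and graded vital signs are only supporting data. The other is that all post-booster safety tables are affected: scheduled safety laboratory samples end 7 days after the first vaccination, and temperature is tabulated as a maximum without a baseline.

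**What to change.** In SAP 5.3, with a cross-reference in 2.1, define emerging vital signs in each post-dose period against the last assessment before that period's vaccination. If the pre-dose reading at that visit is missing, use the last earlier value. For Post-Dose 1 nothing changes.

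Keep the Day 1-referenced tabulation as a supplement, so that abnormalities persisting from an earlier dose are not masked, and label each table with its reference.

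The cost is one extra reference flag in the vital-signs analysis dataset and one additional table. No new data are needed. The main table's reference will then differ by period, which a footnote can state.
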